## 7.5 CONCOMITANT MEDICATIONS

All medications administered within 14 days prior to and during screening will be recorded in the case report form. Medications that are not specifically prohibited are permitted at the Investigator's discretion.

## 7.6 PROHIBITED MEDICATIONS, TREATMENTS, AND PROCEDURES

No medications, treatments, or procedures are prohibited unless specifically mentioned in the eligibility criteria. Patient safety and well-being are paramount: Any treatment deemed necessary may be utilized at the investigators discretion should there be any concern for the patients health.

# 8 ASSESSMENT OF SAFETY

In addition to standard safety monitoring by the sponsor, an independent DSMB will oversee patient safety in the trial. The DSMB will meet as specified in its charter.

## 8.1 SPECIFICATION OF SAFETY PARAMETERS

Mortality, re-hospitalization, and ED visits through 90 days will be assessed for safety as well as efficacy

Hypotension, defined as a SBP < 100mmHg, will be assessed as a safety endpoint. SBP Decrease Safety Margin: Patients whose SBP decreases to < 100mmHg at any time (measurement must be repeated twice, 15 minutes apart, unless symptomatic) or who develop evidence of clinical hypotension (i.e. weakness, dizziness, faint, chest discomfort) despite a SBP > 100mmHg will be immediately assessed and treated as needed, and all further strategy of care interventions will be halted. Patient safety and care is paramount and takes precedence over all other considerations. The clinical team may halt the study at any time. If there are any questions, the PI or designee will make the final decision.

### 8.1.1 DEFINITION OF ADVERSE EVENTS (AE)

The Investigator and study staff are responsible for detecting and recording AEs and SAEs during scheduled safety evaluations and whenever such information is brought to their attention. This section of the protocol provides definitions and detailed procedures to be followed. During each visit, the Investigator will question the patient about adverse events using an open question, taking care not to influence the patient's answers, e.g. "Have you had any unusual symptoms or medical problems since the last visit? If yes, please describe."

An AE is any unfavorable and unintended sign, symptom, or disease temporally associated with the use of an investigational (medicinal) product or other protocol-imposed intervention, regardless of attribution.

This includes the following:

- AEs not previously observed in the subject that emerge during the protocol-specified AE reporting period.
- Complications that occur as a result of protocol-mandated interventions (e.g., invasive procedures such as cardiac catheterizations).
- If applicable, AEs that occur prior to assignment of study treatment associated with medication washout, no treatment run-in, or other protocol-mandated intervention.
- Preexisting medical conditions (other than the condition being studied) judged by the investigator to have worsened in severity or frequency or changed in character during the protocol-specified AE reporting period.
- Abnormal laboratory values that fall into an abnormal range based upon the hospital's laboratory standards, the abnormality was not preexisting prior to enrollment, and the abnormality leads to a new treatment within the AE time frame

The AE and SAE reporting period extends to day 5 of hospitalization or discharge, whichever comes first, unless otherwise specified.

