### 6.1.2 DURATION OF THERAPY

Both arms will continue until 6 hours after randomization. 6 hours was chosen to avoid confounding by patients with overly long ED LOS. At minimum, patients should receive at least one round of treatment. The protocol continues even if patients reach the floor. However, if in the opinion of the investigator, the protocol should not be continued once on the hospital floor, this is allowed and should be marked on the case report form.

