#### 7.3.1 SCREENING

A signed and dated informed consent form will be obtained before any study-specific screening procedures are performed. Results of evaluations obtained as part of routine medical care, which are performed prior to obtaining informed consent, may be used in place of the protocol-specified evaluations. Patients will acknowledge and agree to the use of this information for the study by giving informed consent.

At the Baseline Visit, patients will be assigned by the Internet Web-based Randomization System (IWRS) a unique permanent identification number (referred to as the patient identification number) such that all randomized patients from each center are given consecutive identification numbers by the IWRS in successive order of inclusion. We will utilize the REDCap randomization module. (NOTE: thus each patient will have two ID's – 1) generated by IWRS and 2) blood specimen label)

Prospective study patients will have presented to the hospital for urgent therapy for AHF. Potential patients will be identified either en route to or upon arriving at the ED/hospital. Routine assessments associated with usual patient care may be used for the purposes of screening and may be completed in any order. Study specific procedures must be completed only after Informed Consent is obtained.

Randomization will occur within three hours of patient's arrival to a room within the ED where they can be seen by a physician or the first time AHF treatment is given. Waiting room time does not count against these three hours.

The following procedures will be performed prior to or during Screening:

- Obtain written informed consent (must be performed as the first study-specific procedure)
- Review of prior medical history
- Review of prior and concomitant medications
- Physical examination (including height and weight when reasonably possible)
- Vital signs measurements (includes systolic and diastolic blood pressures, heart rate, body temperature, oxygen saturation reading and respiratory rate)
- 12-Lead Electrocardiogram
- Chest X-Ray (this is not a requirement however, for inclusion)
- Blood collection for local laboratory tests, including BNP or NT-proBNP, and pregnancy test if applicable.
- Inquiry about Adverse events

---

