### 7.3.3 FOLLOW-UP & FINAL STUDY VISIT

Patients will be followed for a maximum of 90 days post-discharge. There will be NO further in-person visits once discharged. Patients will be called however at 30 and 90 days post-discharge ((+) 30 business days or at the discretion of the local site PI to assess vital status and re-hospitalizations or ED visits.

---

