### 7.3.7 SCHEDULE OF EVENTS TABLE

Schedule of Events	Screening	Day 1 T00	Day 1 T02-04	Day 1 T06	Day 2-6 T24-D6	Day 7 or D/C*	30 & 90 day follow up	Quarterly
Informed consent (I/E)	X							
Medical History	X							
Medication history	X							
Clinical Assessment #		X	X	X	X	X		
Body Weight, height, Vital Signs	ED SOC	VS only	VS only	VS only	BW/VS only	BW/VS only		
Labs: Electrolytes, hematology, NP, eGFR, Troponin	ED SOC							
NT-proBNP / hsTroponin (for central lab processing)		X				X		
12-lead ECG	ED SOC							
CXR	ED SOC							
LUS B-lines 8 zone	X (LUS T00)		X	X	X	X		
LUS Guided AHF Management or Usual Care		X	X	X				
Lab draw: eGFR, Hgb/Hct ^		X				X*		
Prep and Storage of Samples		X				X		
eCRF/data collection/verification		X					X	

Assessment of AE/SAE's							X	
Phone follow-up Vital Status							X	
Batch shipment of samples								X
Subject payment		X					X	

SOC = standard of care, ED = Emergency Department, I/E = inclusion, exclusion, CV = cardiovascular, LUS = lung ultrasound, BW = body weight, NP = natriuretic peptide ^if collected as part of standard of care, will use that result. The last collected result will be used if not drawn on or close to discharge \*Day 7 or discharge, whichever comes first. #As documented by clinician during inpatient stay or per form for ED phase

Further detail regarding timing of assessments: [NOTE: given clinical circumstances (i.e. left the ER for a test, discussion with consultant, etc) – the SITE PI has final discretion to continue to image a patient before or after the allotted window. This time MUST be recorded in the eCRF]

- T00: initial LUS scan (in ED for screening and eligibility)
- T02: 2-4 hours after initial treatment (in ED) (+/- 30 minutes)
- T06: 2-4 hours after T02 or pre-ED discharge, whichever comes first (+/- 60 minutes)
- HD2: 24 hours after initial scan (Day 2) (+/- 6 hours)
- HD3: 48 hours after initial scan (Day 3) (+/- 8 hours)
- HD4: Day 4 (anytime during day)
- HD5: Day 5 (anytime during day)
- HD6: Day 6 (anytime during day)
- HD7: Day 7 (anytime during day)

\* NTproBNP/hsTnT blood draw. This should occur within 6 hours of randomization. Ideally, the blood draw should occur as soon as possible after randomization, preferably within 3 hours.

\*\* For vital signs during hospitalization. The nearest vital signs to the LUS exam will be captured.

^HD = Hospital day

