### 8.4 REPORTING PROCEDURES

#### 8.4.1 ADVERSE EVENT REPORTING

The study period during which AEs must be reported begins after informed consent is obtained and initiation of study treatment and for 7 days after ending study treatment. Subject's hospital discharge summaries will be examined at hospital discharge and all non-exempt AEs will be investigated by examining necessary medical records.

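### General AEs and SAEs have no single reporting window: two sections close it at day 5 or discharge, another keeps it open to 7 days after treatment, and the shorter rule depends on length of stay

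*Combined protocol and SAP*

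**What the plan says.** Four places in the protocol bear on the period over which AEs and SAEs are counted.

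- **7.2.1 and 8.1.1** state the same rule: "The AE and SAE reporting period extends to day 5 of hospitalization or discharge, whichever comes first, unless otherwise specified".
- **8.4.1** says that the period for AE reporting "begins after informed consent is obtained and initiation of study treatment and for 7 days after ending study treatment". Section 6.1.2 fixes when treatment ends: "Both arms will continue until 6 hours after randomization".
- **7.3.7**, the schedule of events, has a row "Assessment of AE/SAE's". As extracted, its only mark is in the 30 and 90 day follow-up column. Section 7.3.3 says that patients are called at those times "to assess vital status and re-hospitalizations or ED visits"; AEs are not named.
- **10.4.5** compares safety events by arm but gives no window beyond the study as a whole.

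AE inquiry during the hospital stay is required elsewhere. Section 7.3.1 lists "Inquiry about Adverse events". Section 8.1.1 says "During each visit, the Investigator will question the patient about adverse events using an open question". Section 8.4.1 adds that "hospital discharge summaries will be examined at hospital discharge and all non-exempt AEs will be investigated".

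Section 8.1 sets a separate 90-day horizon for mortality, re-hospitalization and ED visits as safety outcomes.

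**The concern.** The reporting period is part of the AE definition. Section 8.1.1 counts events that emerge within it, and laboratory abnormalities only if they lead to new treatment within it. With two periods, an event on day 6, or on day 4 after a day 3 discharge, is reportable under 8.4.1 and not under 7.2.1 or 8.1.1. Sites acting in good faith could collect different data, and the by-arm tables in 10.4.5 would mix them.

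The shorter rule has a second weakness. Discharge happens after randomization and may be influenced by the strategy, whose stated aim is faster decongestion. A window that closes at discharge gives the arms unequal observation time whenever their stays differ, and simple comparisons of proportions do not correct for that.

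This matters because 10.4.7 allows early halting only on safety grounds, and 2.3.2 looks to this pilot for evidence of sufficient safety before an efficacy trial. The diuretic risks named in 2.3.1 (kidney injury, over-diuresis, electrolyte disturbance) have no horizon of their own, so they rely on this window.

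**Working it through.** **Inputs from the documents.** Rule A (7.2.1, 8.1.1): earlier of day 5 and discharge. Rule B (8.4.1): 7 days after the end of treatment. End of treatment (6.1.2): 6 hours after randomization. The plan gives no figure for AE rate or length of stay, so there is none to reproduce.

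**Step 1: window length.** Write L for length of stay in days and treat day 5 as 5 days.

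- A = min(L, 5)
- B = 7 + 6/24 = 7.25 days at most, whatever L is

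| Stay (days) | A | B | B/A |
|---|---|---|---|
| 1 | 1 | 7.25 | 7.25 |
| 2 | 2 | 7.25 | 3.6 |
| 3 | 3 | 7.25 | 2.4 |
| 5 or more | 5 | 7.25 | 1.45 |

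The rules do not coincide for any length of stay.

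**Step 2: the schedule.** Its single mark falls 30 and 90 days after discharge, when both windows have normally closed. The scans and the samples marked for day 7 or discharge can fall after day 5, so for stays beyond 5 days Rule A closes before the last planned in-hospital assessment.

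**Step 3: effect of unequal stay under Rule A.** Everything here is assumed: mean stays of 4 and 5 days, and the same AE hazard in both arms. With a constant hazard, expected events are proportional to the mean of min(L, 5).

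For exponentially distributed stays with mean m, that mean is m(1 − e^(−5/m)):

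- m = 4: 4(1 − e^(−1.25)) = 2.85 days
- m = 5: 5(1 − e^(−1)) = 3.16 days
- deficit: 1 − 2.854/3.161 = 9.7%

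Gamma-distributed stays with shape 2 and 4 give 10.6% and 11.4%. The deficit reaches 1 − 4/5 = 20% only if every patient stays exactly the mean, so that the cap at 5 days removes nothing.

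If the hazard instead decays as e^(−t), with t in days, the deficits for shapes 1, 2 and 4 are 3.9%, 3.1% and 2.3%.

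**Step 4: proportion with an AE, for identical stays within each arm.** With assumed stays of 3 and 4 days and constant daily hazard h, the proportion with at least one AE is 1 − e^(−hA).

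- h = 0.02: 5.8% vs 7.7%, ratio 0.76
- h = 0.10: 25.9% vs 33.0%, ratio 0.79

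Under Rule B both arms show the same risk: 13.5% at h = 0.02 and 51.6% at h = 0.10.

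**The case against.** The strongest reply is that the text already has a way out. The day 5 rule yields where something else is specified, and 8.4.1 is the section on AE reporting, so it could be read as the specification. That reading is reasonable, but the protocol does not state it. Section 8.4.1 is itself a general rule, it speaks of AEs while the day 5 rule covers AEs and SAEs, and 7.2.1 repeats the day 5 rule without reference to 8.4.1.

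Three stronger readings are tempting, and the documents do not support them.

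- *AEs are assessed only at the 30 and 90 day calls.* This describes the schedule row alone. Inquiry is also required at screening, at each visit and through the discharge summary. The table was read from PDF across a page break, so a lost merged cell cannot be excluded, although the mark lines up with the telephone follow-up row. The conflict between 8.1.1 and 8.4.1 stands without the schedule.
- *Return visits after an early discharge would be missed.* They would be lost only as AEs. ED visits and re-hospitalizations are safety outcomes through 90 days under 8.1. Hypotension is a separately defined safety endpoint, and hypotension during ED treatment falls inside either window.
- *The earlier-discharged arm will look safer by a fifth.* That ignores the 5-day cap and needs a difference in stay between arms, for which the documents give no figure.

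Halting rules and safety oversight are deferred to a DSMB charter that is not among the documents. It may say more, but sites work from the protocol.

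**Conclusion.** The inconsistency is certain on the current text and needs no assumption: general AEs and SAEs have two incompatible reporting windows, a schedule row that fits neither, and an analysis section that names none. It does not extend to mortality, re-hospitalization or ED visits, and it changes no sample-size figure.

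The bias between arms is conditional. It arises only under the day 5/discharge rule and only if length of stay differs by arm. With a one-day difference in mean stay and constant equal hazard, about 10% fewer recorded AEs in the shorter-stay arm is a fair illustration; with early risk it is 2% to 4%. The reason to act is that the rules conflict and one of them depends on discharge, not that a bias of any given size has been shown.

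**What to change.** Reconcile 7.2.1, 8.1.1, 8.4.1 and the schedule to one AE/SAE window of fixed length, identical in both arms and independent of discharge. The rule in 8.4.1 is already independent of discharge, but it starts at consent and treatment initiation and ends relative to the end of treatment, so the start and end points should be stated explicitly. Keep the SAE reporting from consent that the Screen Failures paragraph in 5.3 requires.

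Then:

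- mark AE/SAE assessment at the in-hospital visits in 7.3.7;
- ask at the existing 30-day call for events after discharge within the window, with dates;
- cite the window in 10.4.5 and base the by-arm AE tables on it, with in-hospital events also shown separately.

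The cost is protocol wording and one question on a planned call. The limit is the quality of the post-discharge data. Section 7.3.3 allows the call 30 business days late, or later at the site's discretion. Thirty business days is about 42 calendar days, so recall could reach back 30 + 42 = 72 days. There is no in-person visit after discharge, so laboratory changes and symptomless events in that part of the window will not be detected. The separate in-hospital table is there for that reason; where stays differ, it should be read with the observation time in each arm.

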### 8.1.2 DEFINITION OF SERIOUS ADVERSE EVENTS (SAE)

An AE will be classified as an SAE if:

- It results in death (i.e., the AE actually causes or leads to death).
- It is life threatening (i.e., the AE, in the view of the investigator, places the subject at immediate risk of death. It does not include an AE that, had it occurred in a more severe form, might have caused death).
- It requires or prolongs inpatient hospitalization.
- It results in persistent or significant disability/incapacity (i.e., the AE results in substantial disruption of the subject's ability to conduct normal life functions).

- It is considered a significant medical event by the investigator based on medical judgment (e.g., may jeopardize the subject or may require medical/surgical intervention to prevent one of the outcomes listed above).

## 8.2 CLASSIFICATION OF AN ADVERSE EVENT

### 8.2.1 SEVERITY OF EVENT

The severity of each adverse event must be recorded as 1 of the choices on the following scale:

Mild	No limitation of usual activities
Moderate	Some limitation of usual activities
Severe	Inability to carry out usual activities

An AE that is assessed as severe should not be confused with a SAE.

### 8.2.2 RELATIONSHIP TO STUDY AGENT

Each reported AE will be described by its duration (i.e., start and end dates), regulatory seriousness criteria if applicable, and suspected relationship to study drug in accordance with definitions set forth at each IRB. In general, these relationships are categorized as likely, possible, unlikely and not related. Experience teaches that gray zone instances will arise, and the site coordinators and PIs will be trained to adjudicate possible SAEs in a systematic fashion. To ensure consistency of SAE causality assessments, investigators will apply the following general guideline:

*Yes* - There is a plausible temporal relationship between the onset of the AE and administration of the study drug and the AE cannot be readily explained by the subject's clinical state, inter-current illness, or concomitant therapies; and/or the AE follows a known pattern of response to study drug or the AE abates or resolves upon discontinuation of study drug;

*No* - Evidence exists that the AE has an etiology other than the study drug (e.g., preexisting medical condition, underlying disease, inter-current illness, or concomitant medication); and/or the AE has no plausible temporal relationship to the study drug.

Adjudication of each AE will proceed as follows: First, the coordinator will consult the site PI to review the chart. Next, the PI will contact members of the clinical care team to clarify uncertainty related to inadequate documentation. Third, if the PI is unable to decide for certain if an AE or SAE occurred, he or she will have the option of sending a personal health identifier-stripped, written narrative of the event to the other site PIs who will vote up or down as to whether the event constituted an AE or SAE.

### 8.2.3 EXPECTEDNESS

The following signs, symptoms, observations and events are frequently observed in association with acute heart failure: dyspnea, orthopnea, paroxysmal nocturnal dyspnea, chest pain, fever, hypoxemia, rapid pulse, rapid respiratory rate, dizziness, syncope, altered mental status, confusion, anxiety, generalized weakness, anorexia, nausea, abdominal pain, back pain, early satiety, vomiting, pneumonia, acute renal failure, skin infection, cancer, surgery not related to treatment of pulmonary embolism, electrocardiography abnormalities (atrial arrhythmias, ventricular dysrhythmias, right bundle branch block, and ST and T wave changes), elevated troponin level, elevated BNP or NT ProBNP level, high white blood cell count, pulmonary infiltrate, pleural effusion, cardiomegaly, electrolyte imbalances, need for oxygen therapy, need for vasopressor support, need for blood product transfusion, need for mechanical ventilation (invasive or non-invasive), need for physical or occupational therapy, need for analgesia, need for skilled nursing facility upon

discharge, need for early follow up with physician, escalation of heart failure therapy, need for cardiac catheterization or PA line placement, need for sleep study.

### 8.3 TIME PERIOD AND FREQUENCY FOR EVENT ASSESSMENT AND FOLLOW-UP

All AEs and SAEs will be followed through resolution, stabilization, or until the subject is lost-to-follow-up.

The onset and end dates, duration, action taken regarding study drug, treatment administered, and outcome for each adverse event must be recorded on the CRF for randomized patients. The relationship of each adverse event to study drug treatment and study procedures, and the severity and seriousness of each adverse event, as judged by the Investigator, must be recorded as described below.

### 8.4 REPORTING PROCEDURES

#### 8.4.1 ADVERSE EVENT REPORTING

The study period during which AEs must be reported begins after informed consent is obtained and initiation of study treatment and for 7 days after ending study treatment. Subject's hospital discharge summaries will be examined at hospital discharge and all non-exempt AEs will be investigated by examining necessary medical records.

#### 8.4.2 SERIOUS ADVERSE EVENT REPORTING

All SAE's will be reviewed within 48 hours and all AE's within 7 days of discovery by the Study Monitor (also known as the medical monitor). Any SAE discovery will be reported to the DCC who will then report to the DSMB, who will be unblinded. If placebo treated patient, standard reporting to the IRB will occur. If active treated patient, and deemed to be related to drug, the SAE will be reported to the DSMB chair within 7 business days by email, fax, or phone of any fatal or life-threatening adverse event that is unexpected.

##### 15 Calendar Day Written Report

The Investigator will also be required to notify the IRBs and all participating investigators, in a written Safety Report, of any serious, unexpected AE that is considered reasonably or possibly related to the strategy-of-care arm

